1.1 Study design

Prospective cohort study. Observation and analysis of patients who underwent heart transplantation from Guangdong Provincial People's Hospital from September 2022 to May 2024 were selected according to the following criteria: Guangdong Provincial People's Hospital underwent heart transplantation; healthy control group: from the healthy physical examination population, the physical examination blood routine, urine routine, liver function, kidney function, glycosylated hemoglobin and other indicators were normal; adult patients aged ≥ 18 years old, male and female; the baseline medical records of the patients were complete, including underlying cardiac diseases, comorbidities, hemoglobin, renal function, urine protein quantification, Serum albumin, lactate, C-reactive protein, heart transplantation operation time, preoperative and postoperative medication and blood pressure, blood transfusion history, ICU hospital stay, cardiac ultrasound (including LVEF), etc., were excluded according to the following criteria: patients were younger than 18 years old, and baseline data were missing;

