1.2 Data Collection

Preoperative and postoperative plasma (on the 1st, 2nd, 3rd, 5th, and 7th postoperative days) and urine (within 48 hours after surgery) of patients undergoing heart transplantation from Guangdong Provincial People's Hospital from September 2022 to May 2024 were collected (the supernatant was collected after centrifugation at 3000r/min for 10 min, and the supernatant was divided into -80° C and stored)

The clinical baseline data of patients who met the inclusion criteria were collected, including gender, age, blood pressure, underlying diseases (hypertension, diabetes, hyperuricemia), serum creatinine, eGFR, serum albumin, hemoglobin concentration, glycosylated hemoglobin, cholesterol, triglycerides, high-density lipoprotein, low-density lipoprotein, urine protein, urine red blood cells, urine white blood cells, cardiac surgery time, and length of hospital stay in ICU. Endpoints: AKI within 7 days, death during hospitalization, survival status at days 28 and 90, and need for dialysis

2. Plasma/urine Humanin concentration detection

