(11) The optical density (OD value) of each well was measured sequentially at 450 nm with a microplate reader within 5 minutes after the reaction was terminated

(12) Calculate the concentration: According to the concentration of the standard and the corresponding OD value, the standard curve graph of Humanin is analyzed by Curve Expert 1.4 software, and the concentration of Humanin in the sample to be measured is calculated by using the equation of the standard curve.

3. Statistical methods

SPSS software was used for data processing. Normally distributed continuous data were statistically described as ($\bar{x} \pm s$), and t-test was used for comparison between groups. Counting data are expressed in terms of frequency, percentage (%), and chi-square test. The receiver operating characteristic curve (ROC) was plotted to analyze the diagnostic value of Humanin for AKI after heart transplantation. The Kaplan-Meier method estimated the survival curve, and the Cox regression model evaluated the influencing factors affecting the survival process. The difference was statistically significant, with $P < 0.05$ as the difference.

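### Healthy controls are not balanced on age or sex, and the only between-group method stated for continuous data is an unadjusted t-test, so a demographic imbalance could contribute to a Humanin difference from recipients

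*Protocol*

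**What the plan says.** Protocol section 1.1 (Study design) names two populations: heart transplant recipients at one hospital, and a "healthy control group: from the healthy physical examination population, the physical examination blood routine, urine routine, liver function, kidney function, glycosylated hemoglobin" and other indicators being normal. The only age or sex condition in that list is "adult patients aged ≥ 18 years old, male and female". It is worded for patients; if it also covers controls, it sets a minimum age and admits both sexes. The section gives no matching, no number of controls and no rule for picking them from the check-up population.

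Section 1.2 (Data Collection) says: "The clinical baseline data of patients who met the inclusion criteria were collected, including gender, age, blood pressure", followed by further items. It does not say that the same is recorded for controls. It provides for preoperative and postoperative plasma in recipients.

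Section 3 (Statistical methods) says of normally distributed continuous data that a "t-test was used for comparison between groups", with chi-square for counts. It does not say which groups are meant. It then plans an ROC curve to "analyze the diagnostic value of Humanin for AKI after heart transplantation", Kaplan-Meier curves, and one regression: "the Cox regression model evaluated the influencing factors affecting the survival process". Significance is declared "with $P < 0.05$ as the difference".

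**The concern.** Recipients and check-up attendees with all-normal results reach the study by different routes, and nothing in the protocol makes them alike in age or sex. A t-test has no means of allowing for that. If Humanin varies with age or sex, part or all of an observed difference could come from who was sampled and not from cardiac disease or transplantation. The protocol does not label the contrast as descriptive, so a P value below 0.05 could be read as a disease or transplant effect.

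An unseen SAP might settle the covariates. The way controls are chosen, however, is a design matter that belongs in the protocol, and on the analysis the protocol is not silent: it names an unadjusted test.

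**Working it through.** **What the text provides.** There are two possible safeguards, one in the design and one in the analysis.

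- Design: section 1.1 selects controls by source and normal results. An adult age floor does not balance age, and admitting both sexes does not balance sex.
- Analysis: section 3 names the t-test for continuous data and chi-square for counts. The Cox model is for survival and does not address Humanin in recipients versus controls.

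Neither safeguard is present.

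**What the text does not provide.** There is no sample size, effect size, Humanin SD, age distribution or relation of Humanin to age or sex. So there is no figure of the plan's own to reproduce. The only numerical input from the document is the 0.05 level (two-sided assumed). Everything else below is an assumption and shows only how the mechanism works.

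**Illustration 1: a fixed shift.** Suppose the true group effect is zero, but imbalance alone shifts mean Humanin by d SD, with n per group. By normal approximation:

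P(reject) = P(|Z + d × √(n/2)| > 1.96)

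| n per group (assumed) | d = 0.2 | d = 0.3 | d = 0.5 |
|---|---|---|---|
| 40 (√(n/2) = 4.47) | 14.5% | 26.9% | 60.9% |
| 60 (√(n/2) = 5.48) | 19.5% | 37.6% | 78.2% |

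For example, at n = 60 and d = 0.3 the shift in the test statistic is 0.3 × 5.48 = 1.64, and P(Z > 1.96 − 1.64) is about 37.6%. The nominal rate is 5%.

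**Illustration 2: a shift built from age.** Let r be the correlation of Humanin with age within groups, and g the age gap in SD units, so that d = r × g. The simulation used 3,000 runs per setting and compared the t-test with linear regression on group and age.

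| n per group | r | g | d | t-test, formula | t-test, simulated | age-adjusted, simulated |
|---|---|---|---|---|---|---|
| 50 | 0.3 | 0 | 0 | 5% | 4.5% | 4.8% |
| 50 | 0.3 | 0.5 | 0.15 | 11.7% | 11.6% | 4.1% |
| 50 | 0.3 | 1.0 | 0.30 | 32.3% | 31.7% | 5.1% |
| 50 | 0.5 | 1.0 | 0.50 | 70.5% | 70.8% | 4.6% |
| 100 | 0.3 | 1.0 | 0.30 | 56.4% | 57.5% | 4.9% |

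Over n = 30 to 100, r = 0.2 to 0.5 and g = 0.5 to 1, the formula gives 6.7% to 94.2%. With no age gap the t-test keeps its level. With age in the model the level is kept in every setting simulated.

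**The case against.** The strongest objection is that the protocol never states this comparison. Section 3 does not say which groups the t-test compares. AKI versus no AKI among recipients is an equally natural reading, since the stated Humanin aim is diagnosis of AKI, and sections 1.2 and 2.1 describe specimens from patients only. This stands to the extent that the contrast is inferred and must be worded conditionally. It does not remove the point: a named control group has no purpose without a comparison, and the t-test is the only between-group method given for continuous data.

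Second, covariates are often left to the SAP. That is fair as to model detail, but it does not cover the choice of controls, and an SAP that adjusted would depart from the test named here.

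Third, the illustration rests on assumed group sizes as well as assumed shifts, and nothing in the protocol shows that Humanin varies with age or sex. This stands. A range of 6.7% to 94.2% means that the size is unknown.

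A reader might also infer three stronger points that the protocol does not support:

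- That age and sex are already on file for everyone. Section 1.2 documents them only for included patients, and its list contains surgery time and ICU stay, which controls cannot have.
- That a difference from controls could not be told apart from demographics. The groups also differ by design in cardiac disease and in other health criteria, so demographics need not explain the whole difference.
- That the AKI result is compromised. The ROC, Kaplan-Meier and Cox analyses run within recipients and do not use the controls.

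**Conclusion.** The point holds in conditional form. The protocol neither balances controls on age and sex nor adjusts for them, and its stated test cannot adjust. If Humanin is compared between recipients and controls by that test, an imbalance could contribute to or produce a significant difference.

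How much is not known. The 15% to 78% range requires 40 to 60 per group, a shift of 0.2 to 0.5 SD due to imbalance alone, a two-sided 0.05 test and no true group effect; only the 0.05 comes from the protocol. With no imbalance, or no relation of Humanin to age or sex, the t-test keeps its 5% level. The consequence is confined to the interpretation of the recipient-versus-control contrast.

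**What to change.** 1. State in section 1.1 what the controls are for, and in section 1.2 that age and sex are recorded for controls as well as recipients.
2. In section 3, replace the t-test for this contrast with a linear regression of Humanin on group, adjusted for age and sex, using the preoperative plasma sample in recipients.
3. If controls are still to be chosen, frequency-match them to recipients on age and sex.
4. Report the contrast as descriptive, since adjustment does not remove the other differences between recipients and healthy people.

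The cost is small. Age and sex must be available for controls, and matching is feasible only if selection is still open and the check-up pool is large enough; the protocol does not say whether either is so. If controls are already fixed, adjustment alone remains possible wherever their age and sex are known.

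The adjusted estimate may be slightly less precise. With equal groups and age as the covariate, the ratio of adjusted to unadjusted standard error is about √[(1 + g²/4)(1 − r²)]. Over the assumed ranges above, the worst case is r = 0.2, g = 1: √(1.25 × 0.96) = 1.10, about 10% wider. The best case is r = 0.5, g = 0.5: √(1.0625 × 0.75) = 0.89, about 11% narrower.

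### The complete-baseline-records rule in 1.1 lists items that arise only after transplantation, so read literally it removes deaths in theatre or before ICU admission from the survival cohort

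*Protocol*

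**What the plan says.** Section 1.1 describes a prospective cohort of adult heart transplant recipients. One inclusion criterion is that "the baseline medical records of the patients were complete". A list of what those records contain follows directly, and part of it reads "heart transplantation operation time, preoperative and postoperative medication and blood pressure, blood transfusion history, ICU hospital stay, cardiac ultrasound (including LVEF". The exclusion criteria restate the rule from the other side: "patients were younger than 18 years old, and baseline data were missing".

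Section 1.2 uses the word baseline in a similar way but at a later step. It begins "The clinical baseline data of patients who met the inclusion criteria were collected", and its list ends with "cardiac surgery time, and length of hospital stay in ICU".

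The samples in 1.2 are "Preoperative and postoperative plasma (on the 1st, 2nd, 3rd, 5th, and 7th postoperative days) and urine (within 48 hours after surgery"), so one plasma sample precedes surgery. Besides AKI within 7 days, the endpoints are "death during hospitalization, survival status at days 28 and 90, and need for dialysis". Section 3 (Statistical methods) states: "The Kaplan-Meier method estimated the survival curve, and the Cox regression model evaluated the influencing factors affecting the survival process".

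**The concern.** Eligibility for a prospective cohort should be decided on information available by the start of follow-up. Here part of the eligibility list comes into being only once the operation is over. A recipient who dies on the table has no postoperative medication and no postoperative blood pressure. If that record counts as incomplete, the patient is left out, and the reason for leaving the patient out is the endpoint event itself. The cohort is then selected on early survival.

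What is at stake is the overall mortality estimate and any Cox model built on preoperative or operative factors. Because preoperative plasma is collected, preoperative Humanin could be one of those factors, and a patient who died in theatre could contribute to that model.

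**Working it through.** The protocol gives no figure on this point to reproduce: no mortality rate, no expected number of deaths, and no share of deaths in theatre or before ICU admission. The check is therefore a reading of the text, followed by an illustration on assumed values.

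**Timing of the listed items**

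| Item in the 1.1 eligibility list | When it becomes available | Available for a death in theatre? |
|---|---|---|
| Preoperative medication and blood pressure | Before surgery | Yes |
| Operation time | At surgery | Known at surgery; not the problem here |
| Postoperative medication | After surgery | No |
| Postoperative blood pressure | After surgery | No |
| ICU stay | At least partly after surgery; could include preoperative ICU time | Ambiguous |

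Postoperative medication and blood pressure carry the point. ICU stay is weaker support.

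**Who is affected**

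- A death in theatre or before ICU admission fails the inclusion rule on a literal reading. Nothing in the protocol exempts early deaths.
- A death soon after ICU admission will usually have left some records. Whether that patient is kept depends on how completeness is applied.
- ROC or Cox analyses of postoperative Humanin do not change. These patients have no postoperative sample and could not enter under any rule.

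**Illustration of size (all inputs assumed)**

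Let m be true mortality, q the share of deaths excluded and r the share of survivors excluded. Then

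observed mortality = m(1−q) / [m(1−q) + (1−m)(1−r)],

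which for r = 0 reduces to m(1−q)/(1−mq).

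With r = 0:

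| m | q = 0.02 | q = 0.05 | q = 0.10 |
|---|---|---|---|
| 5% | 0.049/0.999 = 4.9% | 0.0475/0.9975 = 4.8% | 0.045/0.995 = 4.5% |
| 10% | 0.098/0.998 = 9.8% | 0.095/0.995 = 9.5% | 0.09/0.99 = 9.1% |
| 15% | 0.147/0.997 = 14.7% | 0.1425/0.9925 = 14.4% | 0.135/0.985 = 13.7% |
| 20% | 0.196/0.996 = 19.7% | 0.19/0.99 = 19.2% | 0.18/0.98 = 18.4% |

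The understatement runs from 0.1 points (m = 5%, q = 0.02) to 1.6 points (m = 20%, q = 0.10).

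A larger share of early deaths gives a larger shift. At m = 10%, if 2% or 3% of all recipients died before ICU admission (20% or 30% of deaths), the result is (0.10−0.02)/0.98 = 8.2% or (0.10−0.03)/0.97 = 7.2%.

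At m = 10%, with survivors also lost to incomplete records:

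- q = 0.05, r = 0.05: 0.095/(0.095+0.855) = 10.0%, no bias.
- q = 0.10, r = 0.05: 0.09/(0.09+0.855) = 9.5%, understated.
- q = 0.05, r = 0.10: 0.095/(0.095+0.81) = 10.5%, overstated.

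The direction therefore depends on whether deaths or survivors lose the larger share. Nothing in the protocol allows an effect on a hazard ratio to be worked out.

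**The case against.** The best defence is that not applicable is not the same as missing. A patient who dies in theatre never generates postoperative data, so nothing due is absent and the record can be called complete. The defence adds that 1.1 is one long, loosely built sentence, and that 1.2 calls length of ICU stay baseline data for patients already included. Baseline may therefore simply mean chart data. The stated purpose for Humanin in section 3, its diagnostic value for AKI by ROC, is untouched. The effect is also small: at m = 10% and q = 10% the shift is 0.9 points, and the binomial standard error falls to that level only at about 0.10 × 0.90 / 0.0091² ≈ 1,100 patients.

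Part of this stands. The size is unknown and may be small, the postoperative Humanin analyses are unaffected, and ICU stay is ambiguous. The 1.2 list selects nobody, so relabelling it is only editorial.

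The main argument does not remove the point. The protocol nowhere says that items not applicable because of death count as complete. Loose use of the word in 1.2 does not alter the list in 1.1, where postoperative items are named as such inside the rule that decides who enters. A SAP that is not shown here may define time zero or analysis populations, but it would not normally set the eligibility criteria.

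**Conclusion.** The concern holds and is minor. It is certain that post-transplant items sit inside the eligibility rule. That the rule removes deaths in theatre or before ICU admission follows from a literal reading, and the protocol does not show that this happened to any patient.

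If such deaths are excluded and survivors are not, overall mortality is understated: by 0.1 to 1.6 percentage points for assumed mortality of 5% to 20% with 2% to 10% of deaths excluded, and by more if early deaths form a larger share. If survivors are also excluded, the bias may be smaller, absent or reversed. These figures indicate scale only; the protocol cannot settle which applies.

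**What to change.** - In 1.1, limit the completeness criterion, and the matching exclusion, to data available before or at transplantation.
- Move postoperative medication, postoperative blood pressure and ICU stay to a list of follow-up variables with no role in eligibility.
- State that every adult transplant in the window stays in the overall survival analysis, which needs only the transplant date and vital status.
- In 1.2, take length of ICU stay out of the clinical baseline data. This is for consistency only.

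The cost is a few wording changes. The downside is that some retained patients will have incomplete covariates, which the analysis must then handle.

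### Section 1.1 admits only recipients with a complete baseline record, which the Humanin-AKI and survival analyses do not need; the cohort shrinks by an unknown amount and may be selected on severity or postoperative course

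*Protocol*

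**What the plan says.** Section 1.1 (Study design) states completeness twice. As an inclusion condition it asks that "the baseline medical records of the patients were complete, including underlying cardiac diseases, comorbidities, hemoglobin, renal function, urine protein quantification", and the list continues with "Serum albumin, lactate, C-reactive protein, heart transplantation operation time" and "preoperative and postoperative medication and blood pressure, blood transfusion history, ICU hospital stay, cardiac ultrasound (including LVEF), etc". The exclusions are then that "patients were younger than 18 years old, and baseline data were missing". No core set, threshold or tolerance is given.

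Section 1.2 (Data Collection) has its own baseline list for recipients who meet the inclusion criteria. It begins "including gender, age, blood pressure, underlying diseases (hypertension, diabetes, hyperuricemia), serum creatinine, eGFR, serum albumin, hemoglobin concentration", passes through HbA1c and lipids, and ends "urine protein, urine red blood cells, urine white blood cells, cardiac surgery time, and length of hospital stay in ICU". The endpoints there are AKI within 7 days, in-hospital death, survival status at days 28 and 90, and need for dialysis.

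Section 2.1 (Specimen retention) also ties sampling to having met the inclusion criteria.

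Section 3 (Statistical methods) plans a ROC curve "to analyze the diagnostic value of Humanin for AKI after heart transplantation", Kaplan-Meier curves, and a Cox model whose covariates are not named.

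**The concern.** A completeness rule at entry removes the whole patient, not just the missing value. A recipient with a Humanin result and a known AKI status can be lost from the ROC because, say, a lactate value is absent. An analysis plan cannot repair this, since it acts only on patients who were admitted. Because section 2.1 links specimens to eligibility, a recipient who fails the rule may have no stored sample at all.

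Three things are at stake:

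- **Numbers.** This is one hospital over a fixed window, September 2022 to May 2024, so every dropped recipient costs potential AKI events and deaths.
- **Representativeness.** If missing items are related to severity or outcome, the AUC and the survival curve describe a selected subset, not adult recipients at this hospital.
- **Timing.** Some required items exist only after the operation, so entry to the cohort depends partly on what happens during the follow-up being studied.

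**Working it through.** The protocol states no sample size, event count or missing-data rate, so there is no figure of its own to reproduce. The check has four parts.

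**1. Item-by-item comparison of the two lists** (pre- and postoperative medication counted as one item; blood pressure likewise)

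| Required in 1.1 | Named in 1.2? |
|---|---|
| Underlying cardiac disease | No (the examples are hypertension, diabetes, hyperuricemia) |
| Comorbidities | Yes, as underlying diseases |
| Hemoglobin | Yes |
| Renal function | Yes, creatinine and eGFR |
| Urine protein | Yes |
| Serum albumin | Yes |
| Lactate | No |
| C-reactive protein | No |
| Operation time | Yes |
| Medication, pre- and postoperative | No |
| Blood pressure, pre- and postoperative | Yes, without timing |
| Transfusion history | No |
| ICU stay | Yes |
| Cardiac ultrasound/LVEF | No |

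Of 14 items, 6 are not named in 1.2 and 8 are. In the other direction, 1.2 names HbA1c, lipids and urine cells, which 1.1 does not name for recipients. Whether a recipient without HbA1c has missing baseline data cannot be settled from the text.

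**2. What each analysis needs**

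- ROC: a Humanin value and AKI status.
- Kaplan-Meier: follow-up time and vital status.
- Cox: the same two, plus whichever covariates are chosen.

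Only the Cox model could use the 14 items.

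**3. Size of the loss**

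Assumption: each of k items is missing in a proportion m of recipients; m is not in the documents and is varied from 1% to 10%. With gaps that are independent or positively associated:

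- low end (all gaps in the same patients): loss = m
- high end (independent gaps): loss = 1-(1-m)^k

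For example, with m = 2% and k = 14, 1-0.98^14 = 1-0.754 = 24.6%.

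| m per item | Low end | High end, k = 14 | High end, k = 8 (items also in 1.2) |
|---|---|---|---|
| 1% | 1% | 13.1% | 7.7% |
| 2% | 2% | 24.6% | 14.9% |
| 5% | 5% | 51.2% | 33.7% |
| 10% | 10% | 77.1% | 57.0% |

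**4. Direction of any selection**

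Let u be the share of urgent recipients, and mu and me the per-item missingness in urgent and other recipients. With k = 14 and independent gaps, the urgent share after exclusion is u(1-mu)^14 / [u(1-mu)^14 + (1-u)(1-me)^14]. All three inputs are assumptions. For u = 20%:

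- mu = me = 2%: the share stays at 20%.
- mu = 5%, me = 2%: 0.2×0.488 / (0.2×0.488 + 0.8×0.754) = 13.9%.
- mu = 2%, me = 5%: 0.2×0.754 / (0.2×0.754 + 0.8×0.488) = 27.9%.

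Selection can therefore go either way, depending on who lacks data.

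**The case against.** The strongest counter-arguments are these.

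- **The bias is conjecture.** A reader might infer that the rule tilts the cohort away from urgent or unstable recipients, whose work-up may be less complete. The protocol never mentions urgency, and it does not say how often items are missing or in whom. Part 4 of the working shows that the direction follows entirely from the assumed rates. This objection stands: only a risk of selection can be claimed.
- **The large losses need independent gaps.** Items missing together in the same patients would bring the loss down towards m. This also stands, which is why both ends are shown.
- **The lists may not conflict.** The 1.1 list is left open at its end, and the 1.2 list is introduced as examples, so an item absent from one may still be collected. This softens the mismatch but does not remove it: an entry rule with an open-ended list can be applied differently by two assessors.
- **The items may serve the Cox model.** They are plausible covariates. That justifies collecting them, but not dropping patients from the ROC and the survival curve when one is absent.
- **Missing-data handling belongs in the SAP.** That is fair for imputation and sensitivity analyses, and the SAP is not shown. Eligibility is fixed in the protocol.
- **The exclusion sentence joins age and missing data with a conjunction**, so read literally it might require both. The inclusion condition alone still removes anyone with an incomplete record.

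**Conclusion.** The point holds as a defect of eligibility. Section 1.1 removes recipients who could contribute to the ROC and the survival curve. It does so on an open-ended list, six of whose roughly 14 items are not named in the section 1.2 list. ICU stay and postoperative medication and blood pressure are treated as baseline although they arise after transplantation, so the rule can select on postoperative course as well as on severity.

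The size is unknown. At an assumed 1% to 10% missing per item, the loss lies between 1% and 10% if gaps cluster fully, and between 13.1% and 77.1% if 14 items are missing independently. These figures illustrate the rule and do not estimate this cohort. The loss of usable patients whenever any required item is missing follows from the text alone; the amount and the direction of any bias do not.

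**What to change.** 1. In 1.1, delete the complete-record inclusion condition and the missing-baseline exclusion. Include every adult recipient transplanted at the hospital from September 2022 to May 2024.
2. Use each recipient in every analysis for which Humanin and the outcome (with follow-up time, for survival) are available. Kaplan-Meier curves that do not involve Humanin can include everyone with follow-up.
3. Handle missing Cox covariates in the analysis, for example by multiple imputation, with complete records as a sensitivity analysis. The detail can sit in the SAP.
4. Use one closed baseline list in 1.1 and 1.2. Add underlying cardiac disease, lactate, C-reactive protein, medication, transfusion history and cardiac ultrasound/LVEF to 1.2, and settle the status of HbA1c, lipids and urine cells. Label postoperative items as such, not as baseline.
5. If recipients have already been dropped under the rule, restore those with specimens, and report how many were dropped and for which items.

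The cost is a change of eligibility wording, data entry for the recipients now left out (number unknown), and an imputation step. Imputation relies on data being missing at random, and with no event count given it is not known how large a Cox model the data will support. Recipients without a stored specimen cannot be recovered for the ROC.
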